### **8.2.2. Exclusion criteria**

Patients meeting any of the following criteria will not be included in the study:

- 1) Enrollment in an interventional clinical trial during the study observation period since clinical trial participants may have clinical scenarios that deviate from the population of interest.
- 2) Evidence of prior treatment with CDK 4/6 inhibitors (ribociclib or abemaciclib) in the metastatic setting.
- 3) Receipt of treatment indicated for another primary cancer during the study observation period or history of another primary cancer within the USON iKM EHR database.

---

\* Diagnosis of hormone receptor-positive/human epidermal growth factor receptor 2-negative breast cancer (BC) will be determined through a review of iKM's discrete diagnosis fields, which are populated during the routine course of care (International Classification of Diseases [ICD] codes will not be used). To identify patients with metastatic disease status, patients must have at least one of the following indicators: 1) receipt of a numbered LOT, 2) Stage IV disease, 3) Tumor, Node, Metastasis (TNM) staging with M value of 1, 4) record of location of metastatic disease or 5) current or prior disease status containing reference to metastatic disease.

† Visits are defined as physical encounters with the practice, detected by vital sign records. The second and third visits must be observed after the index date to demonstrate continuity of care. There is no required time span between the additional visits and the index date.

4) Initiated first treatment more than 120 days after metastatic date.

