### 8.2.3. Cohort definitions and stratifications

Patients who meet the eligibility criteria described in **Sections 8.2.1-8.2.2** will be classified into the following cohorts described in **Section 8.1**.

As supported by the final sample size, each of the results tables and figures will be stratified to present the data for the following stratifications:

- Menopausal status (pre-, peri-, and post-menopausal) – post-menopausal only
- Metastases (visceral vs. non-visceral, bone only vs. non-bone only)
- Metastatic status (de novo versus relapsed/recurrent)
- Stage at diagnosis (I/II, III, IV or not documented)
- Number of metastatic sites (1, 2 and  $\geq 3$ )
- Prior adjuvant endocrine therapy (both prior to and after metastases)
- Prior adjuvant chemotherapy (both prior to and after metastases)
- Age stratifications (e.g., 18-50, 51-69,  $\geq 70$ ) also  $<65$  years and  $\geq 65$  years
- Race (White, Black, other, not documented)
- Palbociclib starting dose (75 mg, 100 mg, and 125 mg starting dose)
- Eastern Cooperative Oncology Group (ECOG) performance status score (0/1, and 2+) 90 days prior to index
- Disease-free interval from end of adjuvant treatment ( $< 12$  months,  $\geq 12$  months)

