iKM use at practice location	iKM structured data	Eligibility criteria	Baseline	Patients who are treated at USON sites that utilize the full EHR capacities of iKM for their index visit will be eligible for participation in the study; otherwise, patients will be excluded.
Data accessibility	iKM structured data	Eligibility criteria	Baseline	Patients whose data are accessible for research purposes will be eligible for participation in the study; otherwise, patients will be excluded.
Disease characteristics				
Date of initial BC diagnosis	iKM structured data + chart review	Eligibility criteria, Baseline characteristic	Medical history prior to index	
To assess BC diagnoses that occurred prior to index, patients' available medical history in iKM will be searched. The completeness of this history will vary based on the length of disease and the time within the USON. Records may also be incomplete for patients with an initial BC diagnosis that occurred outside of the USON.
 
Diagnosis of BC will be determined through a review of iKM's discrete diagnosis and histology fields, which are populated during the routine course of care (International Classification of Diseases [ICD] codes will not be used).
 
If no initial diagnosis date is documented, the first recorded diagnosis date in iKM will be used. This date will be used in calculations, not reported separately.
 
Patients without a recorded diagnosis of BC will be excluded from the study.

Date of mBC disease diagnosis	iKM structured data + chart review	Eligibility criteria, Baseline characteristic	Medical history prior to index	
Date of first recorded diagnosis of metastatic disease within the EHR. Patients will be qualified initially based on the date identified in the structured data; this will be confirmed during chart review among patients selected for chart review. Ultimately, the primary source will be the chart if available.
 
Patients without recorded evidence of metastatic disease will be excluded from the study.
 
Structured data will confirm the patient as metastatic and as available, indicate the earliest associated date of any of these criteria:
 
 
1) Stage IV disease
 
2) Tumor, Node, Metastasis (TNM) stage with M value of 1
 
3) Record of location of metastatic disease
 
4) Current or prior disease status containing reference to metastatic disease
 

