Time since initial BC diagnosis	iKM structured data + chart review (derived)	Baseline characteristic	Medical history prior to index	The duration of time, in weeks, between the date of BC diagnosis and presentation of metastatic disease will be calculated for each patient and summarized as the mean ( $\pm$ SD) and median (range) of values. The number of patients with available data will be reported.

				Date of BC diagnosis and presentation of metastatic disease will be determined as defined above.
Time since mBC diagnosis	iKM structured data + chart review (derived)	Baseline characteristic	Medical history prior to index	The duration of time, in weeks, between the index date and presentation of metastatic disease will be calculated for each patient and summarized as the mean ( $\pm$ SD) and median (range) of values. The number of patients with available data will be reported. Presentation of metastatic disease will be determined as defined above.
Distant metastatic site(s)	iKM structured data + chart review	Baseline characteristic	Medical history prior to index	Baseline metastatic location(s) will be identified and categorized as: Bone (single) Bone (multiple) Brain Liver (single) Liver (multiple) Lung (single) Lung (bilateral) Lung (pleural effusion) Lymph nodes (regional) Lymph nodes (distant) Ovary Other No information Note, "no information" can indicate that metastases were not documented in the chart, not necessarily that patients did not have metastases.
Endocrine sensitivity at 12 months	iKM structured data	Baseline characteristic	Baseline	Patients who experienced relapse more than 12 months of completing adjuvant endocrine therapy will be considered to be endocrine sensitive; those who relapse in less than 12 months, endocrine resistant.
Endocrine sensitivity at 24 months	iKM structured data	Baseline characteristic	Baseline	Patients who experienced relapse more than 24 months of completing adjuvant endocrine therapy will be considered to be endocrine sensitive; those who relapse in less than 24 months, endocrine resistant.
Visceral/non-visceral status	iKM structured data + chart review (derived)	Baseline characteristic	Medical history prior to index	Categorized as: Visceral (asymptomatic or symptomatic*) Adrenal gland Bronchus Cervix Esophagus Gastrointestinal tract Genital organ Intestinal tract Kidney Large intestine Liver Lung Mediastinum Omentum Other respiratory organ Other urinary organ Ovary Pancreas

PFIZER CONFIDENTIAL

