Comorbidities	Chart review	Baseline characteristic	6 months prior to index	
Comorbidities documented within 6 months prior to or on the index date will be captured and summarized as:
 
Atrial fibrillation Bradyarrhythmia Cerebrovascular disease Congestive heart failure Chronic pulmonary disease Connective tissue disease Dementia Diabetes with end organ damage Diabetes without end organ damage Depression Electrolyte abnormalities Hemiplegia HIV/AIDS Hyperlipidemia Hypertension Infection Leukemia Long QT syndrome (congenital) Long QT syndrome (drug induced) Lymphoma Metastatic solid tumor (other than breast cancer) Mild liver disease Moderate to severe renal disease Myelosuppression Myocardial infarction Peptic ulcer disease
																					

				Peripheral vascular disease Tachycardia Stroke Unstable angina Venous thromboembolism (pulmonary embolism or deep vein thrombosis)
Disease histology	iKM structured data	Baseline characteristic	Baseline	Categorized as: Ductal Lobular Mixed Metaplastic Tubular Mucinous Other No information
Breast cancer gene (BRCA) 1/2 status	Chart review	Baseline characteristic	Medical history prior to index	Categorized as: Positive Negative No information
Estrogen receptor 1 gene (ESR1) status	Chart review	Baseline characteristic	Medical history prior to index	Categorized as: Positive Negative No information
Next generation sequencing (NGS) status	Chart review	Baseline characteristic	Medical history prior to index	Categorized as: Positive Negative No information
Treatment characteristics				
Prior adjuvant hormonal treatment	iKM structured data + chart review	Treatment characteristics	Medical history prior to index	The proportion of patients with prior adjuvant hormonal treatment for breast cancer prior to the index treatment.
Prior neo-adjuvant/adjuvant chemotherapy	iKM structured data + chart review	Treatment characteristics	Medical history prior to index	The proportion of patients with prior neo-adjuvant/adjuvant chemotherapy for breast cancer prior to the index treatment.
Prior metastatic hormonal treatment	iKM structured data + chart review	Treatment characteristics	Medical history prior to index	The proportion of patients with prior metastatic hormonal treatment for breast cancer prior to the index treatment.
Adjuvant treatment end dates	iKM structured data + chart review	Treatment characteristics	Medical history prior to index	Date of adjuvant treatment discontinuation.

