Disease-free interval	iKM structured data + chart review (derived)	Treatment characteristics	Medical history prior to index	The duration (in weeks) between discontinuation of adjuvant therapy and the start of treatment for metastatic disease. The number of patients with available data will be reported.  Findings will be summarized as the mean ( $\pm$ SD) and median (range) of values, along with

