## Palbociclib (IBRANCE)

## Study Number A5481128 NON-INTERVENTIONAL STUDY PROTOCOL

Protocol Version 2, August 30, 2021

				the proportion of patients with a duration less than or greater than/equal to 12 months.
Surgery	Chart review	Treatment characteristics	Medical history prior to index	The proportion of patients who had surgery prior to the index treatment.
Radiotherapy	Chart review	Treatment characteristics	Medical history prior to index	The proportion of patients who received radiation prior to the index treatment.
Index treatment regimen	iKM structured data + chart review	Eligibility criteria, Treatment characteristics	Study observation period	Patients' index treatment will be categorized based on the cohort descriptions in Section 8.1: PB+FUL CCI
Date of treatment initiation during the patient identification period (i.e., index date)	iKM structured data + chart review	Eligibility criteria, Treatment characteristics	Study observation period	The date of initiation with a PB+FUL or CCI during the study identification period. If the combination regimen consists of more than one drug with drugs given on different dates, the date of the first administration of any drug will be used. Patients who did not initiate a qualifying regimen during the patient identification period will be excluded from the study.
Treatment initiation by quarter	iKM structured data + chart review (derived)	Treatment characteristics	Study observation period	The proportion of patients who initiate treatment by quarter.
Index treatment end date(s)	iKM structured data + chart review	Treatment characteristics	Study observation period	Date of final treatment for each drug or regimen. It is possible that the patient's treatment stop date is not documented if the patient dies, is lost-to follow-up or is still on-therapy. The final treatment date, death date or end of study date will be used, whichever is earliest.
Index line of therapy (LOT)	iKM structured data + chart review (derived)	Treatment characteristics	Study observation period	LOT will be assigned based on the absolute chronologic order of regimens, based treatment start and stop dates. Specifically, first-line treatment designation will be assigned to the first treatment received after metastatic diagnosis. Line of therapy will advance with each subsequent regimen.

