Prior metastatic hormonal treatment	iKM structured data + chart review	Treatment characteristics	Medical history prior to index	The proportion of patients with prior metastatic hormonal treatment for breast cancer prior to the index treatment.
Adjuvant treatment end dates	iKM structured data + chart review	Treatment characteristics	Medical history prior to index	Date of adjuvant treatment discontinuation.
Disease-free interval	iKM structured data + chart review (derived)	Treatment characteristics	Medical history prior to index	The duration (in weeks) between discontinuation of adjuvant therapy and the start of treatment for metastatic disease. The number of patients with available data will be reported. Findings will be summarized as the mean (\pm SD) and median (range) of values, along with the proportion of patients with a duration less than or greater than/equal to 12 months.

PFIZER CONFIDENTIAL

Surgery	Chart review	Treatment characteristics	Medical history prior to index	The proportion of patients who had surgery prior to the index treatment.
Radiotherapy	Chart review	Treatment characteristics	Medical history prior to index	The proportion of patients who received radiation prior to the index treatment.
Index treatment regimen	iKM structured data + chart review	Eligibility criteria, Treatment characteristics	Study observation period	Patients' index treatment will be categorized as: PB+FUL CCI
Date of treatment initiation during the patient identification period (i.e., index date)	iKM structured data + chart review	Eligibility criteria, Treatment characteristics	Study observation period	The date of initiation with a PB+FUL or CCI [REDACTED] during the study identification period. If the combination regimen consists of more than one drug with drugs given on different dates, the date of the first administration of any drug will be used. Patients who did not initiate a qualifying regimen during the patient identification period will be excluded from the study.
Treatment initiation by quarter	iKM structured data + chart review (derived)	Treatment characteristics	Study observation period	The proportion of patients who initiate treatment by quarter.

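### The disease-free interval ends at the start of metastatic treatment, so it includes the treatment delay and can move patients from the under-12-month to the 12-month-or-more stratum

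*Protocol*

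**What the plan says.** Protocol Table 2 measures the disease-free interval in weeks, "between discontinuation of adjuvant therapy and the start of treatment for metastatic disease", and reports "the proportion of patients with a duration less than or greater than/equal to 12 months". SAP Table 1 has the same end point: "discontinuation of adjuvant therapy and the start of treatment for metastatic disease". Protocol Section 8.2.3 and SAP Section 4.4 use the same cut as a stratification, "Disease-free interval from end of adjuvant treatment", split at 12 months. It is one of twelve listed stratifications, all conditional on the final sample size.

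Four other entries bear on the point:

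- **Exclusion criterion 4** (Protocol Section 8.2.2, SAP Section 4.1) removes patients who "Initiated first treatment more than 120 days after metastatic date".
- **Endocrine sensitivity at 12 months** (same tables) is measured to relapse: "Patients who experienced relapse more than 12 months of completing adjuvant endocrine therapy will be considered to be endocrine sensitive".
- **The two dates needed for a diagnosis-based interval** are already variables: "Date of adjuvant treatment discontinuation" and "Date of first recorded diagnosis of metastatic disease within the EHR". For the second, the chart is the primary source where available.
- **Time since mBC diagnosis** is a planned variable, from presentation of metastatic disease to the index date.

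Neither document explains why treatment start was chosen as the end point, or plans a check on that choice.

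**The concern.** A patient whose metastatic disease has been diagnosed but not yet treated is no longer disease-free. Under the planned definition that waiting time still counts. In the extreme, a patient who stopped adjuvant therapy on the day metastases were found would have a positive disease-free interval made up entirely of waiting time.

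The added time is never negative, so the error does not average out. It lengthens the summary of the interval and, near 12 months, moves early patients into the late stratum. Results presented by this cut would then have some early patients counted as late. The neighbouring endocrine-sensitivity variable stops at relapse with the same threshold. A patient who relapsed at 10 months and started treatment at 12.5 months would be endocrine resistant on one variable and in the 12-month-or-more stratum on the other.

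**Working it through.** The plan states no expected count or precision for these strata, so there is no figure to reproduce. The check is date arithmetic followed by an illustration.

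**1. What the interval contains.** Let A be the end of adjuvant therapy, M the metastatic diagnosis date and T the start of metastatic treatment.

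Planned interval = T − A = (M − A) + (T − M).

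First-line treatment is defined as the first treatment after metastatic diagnosis. For the first-line cohort, T is therefore the index date, and d = T − M is at least 0. Criterion 4 caps d at 120 days = 120/7 = 17.1 weeks. Protocol Table 3 shows that exclusion among the structured-data steps and not again after chart review, so I assume the cap holds for the date finally used.

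**2. Effect on the mean.** mean(T − A) − mean(M − A) = mean(d), which lies between 0 and 17.1 weeks.

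**3. Who can change stratum.** A patient moves only if M − A < 365.25 ≤ (M − A) + d. With d ≤ 120 this requires M − A ≥ 365.25 − 120 = 245.25 days, or 245.25/30.44 = 8.06 months. Anyone diagnosed earlier stays in the under-12-month stratum. Because d ≥ 0, nobody moves from 12 months or more to under 12. In the example above, the delay of 2.5 months is 2.5 × 30.44 = 76 days, within the cap.

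**4. Size with even relapse times.** Assumption, not in the documents: times to relapse, taken here as the metastatic diagnosis date, are spread evenly over the first 365 days and are unrelated to the delay. The share of the true under-12-month stratum that moves is then mean(d)/365.

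| Mean delay (days) | Calculation | Share moved |
|---|---|---|
| 30 | 30/365 | 8% |
| 60 | 60/365 | 16% |
| 90 | 90/365 | 25% |
| 120 (every patient at the limit) | 120/365 | 33% |

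**5. Size with another shape.** Take exponential times, F(t) = 1 − exp(−ln 2 × t/median), with an assumed median of 12 to 60 months. For a fixed delay g, the share of evaluable patients moved is F(12) − F(12 − g). Dividing by F(12) gives the share of the true under-12-month stratum. Example with a median of 24 months and g = 30 days (0.99 months): F(12) = 0.293, F(11.01) = 0.272, difference 0.020, and 0.020/0.293 = 7%. For counts, I assume that 30% to 70% of the 317 first-line patients in Protocol Table 3 have an evaluable interval.

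| Delay | Share of true under-12-month stratum | Share of evaluable patients | Patients |
|---|---|---|---|
| 30 days for all | 5.9–7.7% | 1.0–2.9% | about 1–7 |
| Uniform 0–120 days | 12–16% | 2.0–6.2% | about 2–14 |
| 120 days for all | 26–31% | 4.1–12.8% | about 4–28 |

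The two shapes give similar shares of the under-12-month stratum.

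**The case against.** The strongest defence is that the definition is explicit, identical in both documents, and of limited reach. It feeds no endpoint and no eligibility rule, and it is not among the example propensity-score covariates. (The Cox model is said to include all variables without listing them, so its role there cannot be told.) The delay is itself reported as time since mBC diagnosis, and a relapse-based 12-month classification is already planned. All of this stands and keeps the point small. It does not correct the stratum: a separately reported delay does not return a misplaced patient, and endocrine sensitivity is not the listed stratification.

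The remedy is also open to challenge. The mBC date is the first recorded in the network's records. It may follow a local recurrence, or a diagnosis made elsewhere, so it is not always the date of first relapse. This is true. For the first-line cohort, however, it is never later than treatment start, so it removes the delay component without adding a new one.

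A reader might infer more than the documents support:

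- **That early relapsers in general are misplaced.** Only those whose own delay spans the cut can move.
- **That a third of them are misplaced.** This needs every delay at the eligibility limit and even relapse times. It is neither an expected value nor a strict ceiling, because relapses clustered just before 12 months would give more.
- **That every table and figure will carry the error.** Stratification depends on the final numbers.
- **That disagreement with endocrine sensitivity proves the error.** That variable starts from the end of adjuvant endocrine therapy, whereas the interval starts from the end of adjuvant therapy generally. It also draws on structured data only. Some disagreement would remain after any fix.

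**Conclusion.** The point holds as a minor flaw of definition. Three things follow from the documents alone, given the 120-day cap and using metastatic diagnosis as the reference: the mean interval is too long by the mean treatment delay; only patients diagnosed about 245 to 365 days after adjuvant therapy can change stratum; and every change is from under 12 months to 12 months or more.

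How many patients move cannot be fixed from the documents. On the assumptions shown, it is roughly 6% to 8% of the true under-12-month stratum at a 30-day delay and 12% to 16% at 60 days or with delays uniform over 0 to 120 days. Figures near a third belong to the extreme case only. Some blurring of the contrast between strata is plausible, but no effect on any stratum estimate has been shown. The primary objectives and all endpoint definitions are untouched.

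**What to change.** In Protocol Table 2 and SAP Table 1, define the disease-free interval as the time from the end of adjuvant therapy to the chart-confirmed date of mBC diagnosis, and use it for the 12-month strata. State the conversion as well, since the interval is in weeks and the cut in months (365.25/7 = 52.18 weeks).

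If treatment start is what the team wants, rename the variable as time from end of adjuvant therapy to first metastatic treatment, and cross-tabulate its 12-month split against the diagnosis-based split.

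No new data are needed. The cost is one line in each table plus the administrative step in the footnote to Protocol Section 8.7: a modified SAP means updating the protocol and sending it back to the IRB. The report should add that the mBC date may still be later than a first local recurrence or a diagnosis outside the network, and that full agreement with the endocrine-sensitivity variable should not be expected.
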